### 3. Reproductive Status

- a. Women of childbearing potential (WOCBP) must agree to use method(s) of contraception.
- b. WOCBP must have a negative serum or urine pregnancy test (minimum sensitivity 25 IU/L or equivalent units of human chorionic gonadotropin [hCG]) within 24 hours prior to the start of investigational product.
- c. Male or non-pregnant, non-lactating female,  $\geq 18$  years of age:
  - i) If sexually active, the patients must agree to use contraception considered adequate and appropriate by the Investigator during the period of trial drug administration. In addition, male and female patients must utilize contraception after the end of the treatment in the individual drugs product's Prescribing Information provided in the trial manual and the Clinical Trial Facilitation Group, provided in [Appendix C](#).

## 4.2 Exclusion Criteria

### 1. Medical History and Concurrent Diseases

- a. Patients with carcinomatous meningitis.
- b. Patients with active central nervous system (CNS) metastases.

- i) Patients are eligible if CNS metastases are adequately treated and neurologically stable at baseline (except for residual signs or symptoms related to the CNS treatment) for at least 2 weeks prior to enrollment. In addition, patients must be either off corticosteroids, or on a stable or decreasing dose of  $\leq 10$  mg QD prednisone (or equivalent) at the time of consent for the trial.
- c. Patients with life expectancy of  $< 3$  months.
- d. Patients with NSCLC with known EGFR mutation or ALK rearrangement.
- e. Patients currently using medicinal or recreational cannabis.
- f. Patients with any serious or uncontrolled medical disorder or active infection with the hepatitis virus or the human immunodeficiency virus (HIV).
- g. Patients with other active malignancies requiring concurrent intervention other than hormone antagonists.
- h. Patients with previous malignancies (except non-melanoma skin cancers and the following in situ cancers: bladder, gastric, colon, cervical/dysplasia, endometrial, melanoma, or breast) are excluded unless a complete remission was achieved at least 2 years prior to trial entry AND no additional therapy other than hormone antagonists is required or anticipated to be required during the trial period.
- i. Patients with a condition requiring systemic treatment with either corticosteroids ( $> 10$  mg QD prednisone equivalent) or other immunosuppressive medications at the time of consent for the trial. Inhaled or topical steroids and adrenal replacement steroid doses  $> 10$  mg QD prednisone equivalent are permitted in the absence of active autoimmune disease.
- j. Patients with known prior history of hemophagocytic lymphohistiocytosis (HLH).
- k. Patients with active known or suspected autoimmune disease or medical conditions requiring systemic immunosuppression. Patients with vitiligo, Type I diabetes mellitus, residual hypothyroidism requiring hormone replacement, or conditions not expected to recur in the absence of an external trigger are permitted to enroll.
- l. Patients with  $> \text{Grade 1}$  (NCI-CTCAE v.4.03) toxicities attributed to prior anti-cancer therapy other than alopecia and fatigue prior to randomization.
- m. Patients who have received therapy with anti-tumor vaccines or other immune-stimulatory antitumor agents. Non-cancer vaccines (non-attenuated and non-live) are permitted.
- n. Patients who have received therapy with anti-PD-1, anti-PD-L1, anti-PD-L2, anti-CD-137, and/or anti CTLA-4 antibodies (including ipilimumab) or any other antibody or drug specifically targeting T-cell co-stimulation or checkpoint pathways.
- o. Patients with a history of symptomatic interstitial lung disease.
- p. Patients not completely recovered from the effects of major surgery or significant traumatic injury at least 14 days before the first dose of trial treatment.

## 2. Physical and Laboratory Test Findings

- a. Patients with active Hepatitis B or C infections.
- b. Patients with a known seropositive test for HIV.

**3. Allergies and Adverse Drug Reaction**

- a. Patients with a history of severe hypersensitivity reactions to monoclonal antibodies.
- b. Patients with a history of allergy or intolerance (unacceptable AE) to trial drug components or Polysorbate-80-containing infusions.

**4. Sex and Reproductive Status**

- a. WOCBP who are pregnant or breastfeeding.
- b. Women with a positive pregnancy test at enrollment or prior to administration of trial drug.

**5. Prohibited Treatments and/or Restricted Therapies**

- a. Patients requiring ongoing or planned administration of anti-cancer therapies other than those specified in this trial.
- b. Patients requiring the use of corticosteroids or other immunosuppressive medications (>10 mg QD prednisone equivalent for more than 14 sequential days). Corticosteroids or other immunosuppressive medications for more than 14 sequential days require approval of the Medical Monitor.
- c. Patients receiving any investigational agent within 28 days of first administration of trial treatment.

**6. Other Exclusion Criteria**

- a. Patients with any other serious or uncontrolled medical disorder, active infection, physical exam finding, laboratory finding, altered mental status, or psychiatric condition that, in the opinion of the Investigator, would limit the individual's ability to comply with the trial requirements, substantially increase risk to their well-being, or impact the interpretability of trial results.

## **5.0 PATIENT ENROLLMENT**

Before patients may be entered into the trial, all patients or legally acceptable representatives must personally sign and date, and receive a copy of the ICF before any trial-specific screening procedure is performed that is not part of standard medical practice.

All patients who enter into the screening period of the trial (defined as the point at which the patient signs the informed consent) will receive a patient identification number (PIN). This number will be used to identify the patient throughout the trial and must be used on all trial documentation related to that patient. The PIN will remain constant throughout the entire trial; it will not be changed at the time of enrollment. A patient is considered enrolled on this trial when s/he signs the IRB-approved informed consent (ICF). A patient will need to pass the screening assessments/procedures before being randomized to 1 of 2 trial arms and then dosed accordingly.

### **5.1 Treatment Arms**

Patients will be randomized in a 1:1 ratio into 1 of 2 arms according to histology type (squamous vs non-squamous) and smoking history (current smokers vs former smokers vs never smokers) as follows:

- Arm 1: Patients will receive AM0010 and nivolumab
- Arm 2: Patients will receive nivolumab alone.

Note: For the purposes of randomization, current smokers will include patients who are currently using any form of tobacco, former smokers will include patients with a prior history of any form of tobacco use, and never smokers will include patients with no history of any form of tobacco use.

## **6.0 TREATMENT PROCEDURES**

AM0010 will be the only non-FDA-approved drug used in this trial.

### **6.1 Investigational Product Dosage, Administration, and Schedule**

AM0010 is provided by Lilly. AM0010 is provided as a sterile, single-use prefilled syringe, with a clear solution. The AM0010 drug product is stored refrigerated. Refer to the product label for full storage instructions.

A pharmacy guide will be provided, which contains details regarding packaging, labeling, storage, (re)ordering, and administration of AM0010.

A trial-defined AM0010 and nivolumab treatment will begin on trial day 1. Patients on Arm 1 will dose with AM0010 prior to initiation of nivolumab dosing. Patients on Arm 1 will dose AM0010 according to their weight:

≤80 kg body weight = 0.8 mg

>80 kg body weight = 1.6 mg.

AM0010 dose recalculations are only required if a patient's body weight changed from ≤80kg to >80kg or vice versa. Change in bodyweight should be calculated based on change from baseline weight or last weight taken per protocol.

Patients will be trained to self-administer AM0010 and will self-administer the dose throughout the trial starting with the first dose. A patient's caregiver may also be trained to perform SQ injections. Both the patient's and caregiver's training must be recorded in the patient's medical records. The Investigator or a qualified designee must be present during administration of the first dose. An AM0010 administration diary must be kept for dosing compliance monitoring.

### **6.2 Nivolumab Administration**

Nivolumab should be obtained by each site as per routine institutional practice. Sites will be responsible for storage and destruction of nivolumab. For preparation and complete prescribing information, refer to the most current prescribing information in the region. Investigators or designees will review the patient's hematology and chemistry panels, liver function tests (LFTs), and the incidence of hematologic and non-hematologic toxicities prior and during study treatment.

Nivolumab will be administered on Day 1 of each 14-day cycle (240 mg Q2W) or 28-day cycle (480 mg Q4W).

Medications used to treat nivolumab-related infusion reactions (eg, diphenhydramine, acetaminophen/paracetamol, corticosteroids) are considered non-investigational medicinal products (NIMPs) and will not be provided by the sponsor. These will be obtained by the investigational sites as marketed products, which should be stored in accordance to the package insert.

Nivolumab is supplied as a 40-mg/4 mL single-dose vial (NDC 0003-3772-11) or a 100-mg/10 mL single-dose vial (NDC 0003-3772-12). Vials should be stored refrigerated. Refer to the product label for full storage instructions.

[figure not shown]
### 6.3 Dosing Schedule

Patients will be treated on an outpatient basis with AM0010 plus nivolumab or nivolumab alone.

Arm 1 consists of AM0010 at 0.8 mg for patients  $\leq 80$  kg body weight or 1.6 mg for patients  $> 80$  kg body weight, self-administered SQ QD (abdomen, thigh, or back of upper arm) plus nivolumab 240 mg over approximately 30 minutes IV infusion Q2W or 480 mg over approximately 30 minutes IV infusion Q4W.

Arm 2 consists of nivolumab alone at 240 mg over approximately 30 minutes IV infusion Q2W or 480 mg over approximately 30 minutes IV infusion Q4W.

Crossover of patients from nivolumab Q2W schedule to Q4W schedule during the study is acceptable. A complete nivolumab cycle (4 weeks; ie 2 doses of nivolumab 240 mg in a cycle) should be completed before such crossover.

Abbreviations: IV = intravenous; Q2W = every 2 weeks; Q4W = every 4 weeks; QD = daily; SQ = subcutaneous.

Note: AM0010 is NOT cycle-dependent for either schedule of nivolumab.

**Figure 2. Dosing Schedule**

Patients will continue on treatment until they experience progressive disease per Investigator assessment, unacceptable toxicity, require subsequent anticancer therapy, withdraw consent, or their physician feels it is no longer in their best interest to continue on treatment.

Crossover of patients from the nivolumab-only treatment arm (Arm 2) into the nivolumab plus AM0010 treatment arm (Arm 1) is permitted at the time of disease progression (as

assessed by the Investigator). Supportive care per the institution’s normal standard of care, including concomitant medications, can be provided at the Investigator’s discretion.

The documentation of the investigational product administration (AM0010) will be noted on the case report form (CRF) page and in the source documentation/patient diary. The date, dose volume, dose amount, and time of administration for each dose when the PK samples are collected (including the 2 days dosing history prior to a PK draw day), the first and last administered dose for the patient, doses withheld and missed, and dose schedule adjustments will be recorded on the respective CRF page. Details of preparing and administering AM0010 will be provided to the patient and are included in the Pharmacy Binder provided by the Lilly/designee.

**6.4 Treatment Withhold, Dose or Schedule Reduction, or Discontinuation for Toxicity**

If an AE occurs, the Investigator should determine if the AE could be attributed to either drug (AM0010 or nivolumab) or both, or if other factor(s) were the cause of the AE. Continued treatment with either drug is based on the Investigator’s assessment of risk-benefit per the guidelines outlined below. Both the study drugs in Arm 1 should be discontinued if 1 study drug is discontinued.

**6.4.1 Treatment Withhold**

**AM0010**

AM0010 dosing will be withheld or permanently discontinued based on the criteria below:

**Table 2: Toxicity Management Guideline for AM0010**

| Toxicity/Adverse Event                                       | Toxicity Grade (CTCAE) or Conditions   | Action Taken to AM0010                                  |
|---|---|--|
| Fatigue   | Grade 3 or 4  | Withhold   |
| AST, ALT  | Grade 3 or 4
>5 to 10×ULN for >2 weeks; drug-related
>10×ULN; drug-related        | Withhold
Permanently discontinue
Permanently discontinue |
| Total bilirubin   | Grade 3 or 4
>5×ULN; drug-related  | Withhold
Permanently discontinue                            |
| Concurrent AST or ALT and total bilirubin elevation                 | AST or ALT>×ULN and total bilirubin >2×ULN; drug-related                                | Permanently discontinue  |
| Alkaline phosphatase  | Grade 3 or 4  | Withhold   |
| Diarrhea, nausea, vomiting, abdominal pain, or bloating             | Grade 3 or 4  | Withhold   |
| Other non-hematologic toxicities with an impact on organ function   | Grade 3 or 4  | Withhold   |
| Skin drug-related AE  | Grade 3 or 4  | Withhold   |
| Any adverse event, laboratory abnormality, or inter-current illness | Presents a substantial clinical risk to the patient in the judgment of the Investigator | Permanently discontinue  |
| Any adverse event including laboratory abnormalities, except        | Grade 4; drug-related   | Permanently discontinue  |

| Toxicity/Adverse Event  | Toxicity Grade (CTCAE) or Conditions   | Action Taken to AM0010              |
|---|--|-------------------------------------|
| 
 
Grade 4 neutropenia <math>\leq</math>21 days
 
Grade 4 lymphopenia or leukopenia <21 days
 
 |  |                                     |
| Any event   | Life-threatening and related   | Permanently discontinue             |
| Any adverse event, laboratory abnormality, or inter-current illness that, in the judgment of the Investigator, warrants delaying the dose             | Grade $\geq$ 2   | Withhold                            |
| Any dosing delay  | Lasting >12 weeks  | Permanently discontinue             |
| Thrombocytopenia  | Grade 3 or 4
Grade 3 or 4 thrombocytopenia with Grade 3 or 4 bleeding; drug-related | Withhold
Permanently discontinue |
| Anemia  | Grade 3 or 4   | Withhold                            |

Abbreviation: G-CSF = granulocyte colony-stimulating factor.

Notes:

- AM0010 doses may be withheld for  $\leq$ 12 weeks (ie, up to 84 consecutive doses).
- AM0010 doses should be withheld until resolution to Grade 1 or pretreatment baseline.
- Withholding dose to allow prolonged steroid tapers to manage drug-related adverse events are allowed.
- Patients receiving AM0010 may receive growth factors (including G-CSF and erythropoietin) for febrile neutropenia or Grade 3 or greater anemia at the discretion of the Investigator.
- Tumor assessments should continue as per protocol even if dosing is withheld.
- See [Table 3](#) for dose schedule reduction criteria for AM0010.

### **Nivolumab**

Delay in nivolumab dosing will be based on the most current package insert. This document can be downloaded from the following Web sites:

FDA home page:

<https://www.accessdata.fda.gov/scripts/cder/daf/index.cfm?event=overview.process&ApplNo=125527>

DailyMed: <https://dailymed.nlm.nih.gov/dailymed/drugInfo.cfm?setid=f570b9c4-6846-4de2-abfa-4d0a4ae4e394>

Please ensure you are using the most current version of the package insert as updates by drug manufacturers are continuous.

Patients may resume treatment with nivolumab when drug-related AE(s) resolve(s) to Grade  $\leq$ 1 or baseline value, with the following exceptions:

- Patients may resume treatment in the presence of Grade 2 fatigue.
- Patients who have not experienced a Grade 3 drug-related skin AE may resume treatment in the presence of Grade 2 skin toxicity.
- Patients with baseline AST/ALT or total bilirubin in the Grade 1 toxicity range who require dose delays for reasons other than a 2-grade shift in AST/ALT or total bilirubin may resume treatment in the presence of Grade 2 AST/ALT or total bilirubin.

- Drug-related pulmonary toxicity, diarrhea, or colitis must have resolved to baseline before treatment is resumed. Drug-related endocrinopathies adequately controlled with only physiologic hormone replacement may resume treatment.

Patients who do not meet the minimum re-treatment criteria on Day 28 of the cycle and do not meet the criteria for discontinuation will delay treatment and be followed for resolution of toxicity to levels specified in the package insert for resuming nivolumab. Cycles may also be delayed for logistic or personal reasons, but patients who have not received therapy for >12 weeks from the scheduled start of cycle should be discontinued from AM0010 and/or nivolumab treatment unless:

- The patient is clinically benefiting from therapy, defined as radiographic or symptomatic improvement in the opinion of the Investigator, and
- Prior approval must be obtained from Lilly or the designee medical monitor in collaboration with the Investigator.

**6.4.2 Dose or Schedule Modifications for Toxicities**

**AM0010**

For Grade 3 or 4 toxicities that are related to AM0010 and do not require dose discontinuation, dose schedule reduction will be performed according to [Table 3](#).

**Table 3. Dose and Dose Schedule Reduction of AM0010**

| Dose Schedule                   | Schedule Modification Criteria | AM0010                         |
|---------------------------------|--------------------------------|--------------------------------|
| SC QD (continuous daily dosing) | -                              | Starting Dose Schedule         |
| 5 Days on/2 days off            | 1st Grade 3 or 4 event(s)      | First Dose Schedule Reduction  |
| 4 Days on/3 days off            | 2nd Grade 3 or 4 event(s)      | Second Dose Schedule Reduction |
| 2 Days on/5 days off            | 3rd Grade 3 or 4 event(s)      | Third Dose Schedule Reduction  |

Abbreviations: QD = daily; SC = subcutaneous

Dosing will be withheld until return of the AE to Grade 1 or baseline. If Grade 3 or 4 toxicity occurs after 3 dose reductions of AM0010, patients will be discontinued from study. Once the dose schedule has been reduced, it should not be increased.

**Nivolumab**

Dose reduction is not permitted for nivolumab.

**6.4.3 Toxicity**

Toxicities will be graded and reported according to the NCI-CTCAE version 4.03 ([Appendix F](#)). This document can also be downloaded from the Cancer Therapy Evaluation Program (CTEP) home page:

[http://ctep.cancer.gov/protocolDevelopment/electronic\\_applications/ctc.htm#ctc\\_50](http://ctep.cancer.gov/protocolDevelopment/electronic_applications/ctc.htm#ctc_50).

#### **6.4.4 Dose Discontinuation for Toxicities**

##### **AM0010**

- Dose discontinuation criteria for AM0010 are provided in [Table 2](#).

##### **Nivolumab**

Withhold or permanently discontinue nivolumab as per the most recent package insert. Patients with combined Grade 2 AST/ALT and total bilirubin values meeting discontinuation parameters should have treatment permanently discontinued.

If treatment is delayed >12 weeks, the patient must be permanently discontinued from nivolumab.

#### **6.4.5 Data Monitoring Committee**

No data monitoring committee will be formed for this trial. Safety will be evaluated on an ongoing basis.

#### **6.5 Concomitant Medication**

Throughout the trial, Investigators may prescribe any concomitant medications or treatments deemed necessary to provide adequate supportive care except for the following:

- Use of systemic anti-cancer therapies (eg, chemotherapy, investigational agent) other than those specified in this protocol are not allowed. Palliative radiation is permitted to non-targeted lesions.
- Immunomodulatory agents including but not limited to anti-CTLA4, anti-PD1, anti-PD-L1, sipuleucel-T, cyclosporine, and tacrolimus.
- Coumadin
- Patients on coumadin should be changed to SQ administered low-molecular weight heparin (LMWH) or oral Factor II or Xa inhibitors with a  $t_{1/2}$  of less than 24 hours.
- Factor II or Xa inhibitor with a  $t_{1/2}$  of greater than 24 hours.
- High-dose steroids (eg, dexamethasone >10 mg/day for more than 14 sequential days).

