The response rate of the combination of AM0010 with pembrolizumab in a small number of NSCLC and RCC (n=5 and 8, respectively) was 2-fold over the expected response rate of pembrolizumab alone, progression free and overall survival was increased even stronger. Preliminary results from a combination of nivolumab and AM0010 appear to support this observation.

AM0010 induces an expansion of novel T-cell clones in patients. This expansion was similar in patients treated with pembrolizumab and AM0010 at 1 mg (10 µg/kg) and 2 mg (20 µg/kg), respectively. This and a comparable ORR on the cohorts treated with AM0010 at 1 mg (10 µg/kg) and 2 mg (20 µg/kg) provide a rationale for a threshold-based fixed dose in Phase 2 and 3 trials.

AM0010 has an acceptable safety profile and encouraging clinical activity in RCC, NSCLC, and PDAC. In addition, the safety profile of anti-PD-1 and AM0010 show mostly non-overlapping TRAEs. In particular, immune checkpoint blockade frequently causes autoimmune toxicity, including colitis, gastritis or pneumonitis and endocrine disruptions, limiting the tolerability of combinations of immune checkpoint inhibitors. AM0010 monotherapy did not cause autoimmune toxicity. As a consequence, the combination of AM0010 with nivolumab (or another anti-PD-1 immune checkpoint inhibitor) was well tolerated (Section 1.2.3.1). The safety profile of AM0010 with PD-1 inhibitors may be better tolerated than combinations of 2 or more immune checkpoint inhibitors. PEGylated IL-10 (AM0010) offers a potent novel and non-redundant mechanism, adding to the arsenal of clinically active immune-oncology drugs. The direct activation of the CD8+ T cells by AM0010 in absence of immune-related adverse events (AEs) should enable combinations with other immune-therapies which block inhibitory mechanisms.

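### Section 6.5 bars long high-dose steroid courses throughout the trial, with no exception for treating drug-related adverse events

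*Protocol*

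**What the plan says.** Protocol Section 6.5 gives a broad permission followed by a list of exclusions: "Throughout the trial, Investigators may prescribe any concomitant medications or treatments deemed necessary to provide adequate supportive care except for the following". One entry in the list is "High-dose steroids (eg, dexamethasone >10 mg/day for more than 14 sequential days". The entry names no arm and does not mention adverse event management.

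The notes to Table 2 in Section 6.4.1, which govern AM0010, say: "Withholding dose to allow prolonged steroid tapers to manage drug-related adverse events are allowed". They allow AM0010 to be withheld for up to 12 weeks (84 daily doses) and set no cap on the steroid dose or on its duration. Neither section cites the other.

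The nivolumab part of Section 6.4.1 begins "Delay in nivolumab dosing will be based on the most current package insert". On restarting it says "Drug-related pulmonary toxicity, diarrhea, or colitis must have resolved to baseline before treatment is resumed". It does not mention steroid tapers. Section 6.2 names corticosteroids once, for infusion reactions: "Medications used to treat nivolumab-related infusion reactions (eg, diphenhydramine, acetaminophen/paracetamol, corticosteroids".

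**The concern.** Both arms receive nivolumab, and the protocol's own rationale (Section 1.3) states that "immune checkpoint blockade frequently causes autoimmune toxicity, including colitis, gastritis or pneumonitis and endocrine disruptions". Long steroid courses for such events are therefore foreseeable, and the Table 2 note shows that the sponsor foresaw them for AM0010.

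Read as written, Section 6.5 leaves a site with two choices when a drug-related event needs high-dose steroids for more than 14 days in a row. It can shorten the course, or it can give the course and depart from the protocol. Section 8.1 lists a significant protocol deviation among the possible reasons for removing a patient, so a departure may have consequences. This is a stated rule pointing the wrong way, and not merely a missing detail.

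**Working it through.** The plan gives no figure to reproduce, so the check is a comparison of texts followed by an illustration of how far they overlap.

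**Step 1: scope of the bar.** Section 6.5 applies throughout the trial. It names no arm, so it covers Arm 1, Arm 2 and crossover patients. Its list is framed as the exception to supportive care. General statements about supportive or appropriate care (Sections 6.3, 9.1.1 and 9.3) therefore do not lift it.

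**Step 2: is there an exception elsewhere?**

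| Place | What it covers | Lifts the 6.5 bar? |
|---|---|---|
| Table 2 notes (6.4.1) | Withholding AM0010 during a long taper | Not expressly; AM0010 only |
| Nivolumab text (6.4.1, 6.4.4) | Delay, withholding and stopping per package insert | No |
| Section 6.2 | Corticosteroids for infusion reactions, no duration given; general reference to prescribing information | No |
| Exclusion 5.b (4.2) | Medical Monitor approval beyond 14 days | No; an entry criterion that 6.5 does not cite |

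No text lifts the bar. In AM0010 recipients one text expects long tapers while another bars some of them. In patients on nivolumab alone there is only the bar.

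**Step 3: how much do the texts overlap?** The documents give no taper schedule. Assume a straight-line taper from D0 mg/day of dexamethasone to zero over T days, and take the 6.5 example (above 10 mg/day for more than 14 days) as the threshold.

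- Days above 10 mg/day = T × (1 − 10/D0).
- The course is barred if this exceeds 14, that is, if T > 14 / (1 − 10/D0).

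| D0 (mg/day) | Barred if T exceeds (days) |
|---|---|
| 10 or less | never |
| 12 | 14 / 0.1667 = 84.0 |
| 16 | 14 / 0.375 = 37.3 |
| 20 | 14 / 0.5 = 28.0 |
| 24 | 14 / 0.5833 = 24.0 |
| 32 | 14 / 0.6875 = 20.4 |

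For example, 24 mg/day over 28 days gives 28 × (1 − 10/24) = 16.3 days above 10 mg/day. That fits inside the 84-day AM0010 withhold, but 6.5 bars it. A taper from 20 mg/day over 21 days gives 21 × 0.5 = 10.5 days and satisfies both texts. The overlap is real but partial.

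**The case against.** The strongest reply is that the Table 2 note is the specific rule and Section 6.5 the general one, so an ordinary reading reconciles them. On its literal words the note permits only withholding a dose, so it authorises no steroid course that 6.5 forbids. This has weight: it is why the point is put as a tension and not as a flat contradiction. But the protocol does not state that precedence, and the note cannot help a patient on nivolumab alone.

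A second reply is that nivolumab toxicity is left to the package insert, and that Section 7.5 refers to intolerance not manageable through the protocol, the package insert or supportive care. The absence of taper wording in the protocol therefore does not show that toxicity guidance is absent. That is correct. The insert's content is not available here, and nothing in the protocol makes it override 6.5.

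A third is that nobody is told to stop steroids early. Section 6.4 leaves continued treatment to the investigator's risk-benefit judgement, and Section 9.3 requires appropriate care after withdrawal for an adverse event. Exclusion 5.b also suggests that the sponsor would accept longer use with approval. These make harm less likely. They do not change the wording of 6.5, which still treats such a course as prohibited.

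Finally, the affected courses are few in kind: many tapers satisfy both texts, as the illustration shows. That stands, and it limits the size of the point.

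**Conclusion.** The point holds in limited form. Section 6.5 prohibits a class of steroid courses with no exception for drug-related adverse events. For AM0010 recipients this is in tension with the Table 2 note; for nivolumab alone it is an unqualified prohibition. Only courses above the 6.5 level for more than 14 consecutive days are affected. It is worth correcting for patient care, and it does not threaten the trial's results.

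Three stronger readings are tempting, and the documents do not support them.

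- **A direct conflict with Table 2 in both arms.** The note concerns AM0010 dosing, so it does not reach patients who receive only nivolumab.
- **A count of affected patients.** Section 1.1 cites Grade 3 or 4 treatment-related event rates of 7% and 10% on nivolumab. These are events of any type, not steroid-treated ones, and the share needing a barred course is not given. Nor do they set a ceiling, because nothing limits steroid need to Grade 3 or 4, and Table 2 allows withholding from Grade 2. The number cannot be derived and may be zero.
- **An effect on efficacy or a bias between arms.** Efficacy is analysed by intention to treat, and steroid use is not among the listed (non-exhaustive) per-protocol exclusions in SAP Section 6.1.1. SAP Section 6.4.6 already plans a separate summary of steroid use. An imbalance in violations is possible but not shown.

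The illustration rests on an assumed straight-line taper and on treating the example in 6.5 as the threshold.

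**What to change.** Keep the existing 6.5 bullet and add at its end: *except to manage AM0010- or nivolumab-related adverse events in either arm*. This keeps the restriction on other long high-dose steroid use and removes the tension with Table 2.

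No matching taper sentence is needed in the nivolumab part of Section 6.4.1. That text already delays restart until the named toxicities resolve. A new sentence would also have to rest on 12-week limits that differ within the protocol: Section 6.4.1 allows an approved exception for a patient who is benefiting, while Section 6.4.4 says "If treatment is delayed >12 weeks, the patient must be permanently discontinued from nivolumab".

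The cost is one clause in a protocol amendment, with the investigator agreement and IRB approval that Sections 12.3 and 13.1 require. Exclusion 5.b, the SAP and data collection stay as they are.
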